## 4. ABSTRACT

*Should not exceed 200 words and should include:*

- *The importance of the research topic*
- *The research hypothesis, question or statement, specific objectives and the significance of the outcome*
- *OUTLINE* *the methods that will be used to accomplish the research specific objectives*

### Background

Prevalence of surgical site infections in cardiac surgery is about 10%. About 3% of patients who develop an SSI will die as a result. Multiple studies confirm that SSIs are a complication with significant sequelae, such as longer hospitalisation, increased health costs, increased morbidity and mortality. Hence, the prevention and management of wound infections in median sternotomy incisions after adult cardiac surgery are crucial for optimizing patient outcomes,

### Aim

To assess the effect of the silver dressing on SSIs rates in adult patients post cardiac surgery.

### Methodology

A single center randomized control trial approach will be employed. Adult patients admitted post cardiac surgery with a sternotomy incision will be randomized into the intervention (n=75) or control group (n=75). Units will include the cardiac surgical intensive care unit, the coronary care unit and the cardiovascular telemetry unit. Intervention will include the use of a silver dressing on the sternotomy incisions and the donors sites where applicable. The control group will follow standard care processes. Data collection will include a checklist and the modified Parsonnet Score. Data analysis will include descriptive and inferential statistics.

### Conclusion

The current rate of surgical site infection amongst cardiac surgical patients is 2.1 below the benchmark of 2.9 with an operational goal of 2.1.

**Introduction**

*May include background information related to the research topic (Importance of the topic), the purpose in carrying out this research, and the importance of potential (expected) findings.*

**BACKGROUND**

Worldwide, cardiovascular diseases are considered the primary contributor to global mortality. Annually, around 18 million individuals die from these diseases, with 85% of the fatalities attributed to heart attacks (Magnussen et al., 2023). The management of cardiac diseases involves either clinical or surgical approaches. Surgical interventions are chosen when they present a greater likelihood of cardiac rehabilitation compared to clinical treatments. As a result, surgeries are quite common and necessitate meticulous planning for nursing care during the postoperative phase. This planning should be based on evidence-based practices to guarantee the delivery of high-quality care to patients. Furthermore, it aims to proactively prevent complications associated with the procedure, including the occurrence of Surgical Site Infections (SSIs) (Pivoto et al., 2010; Vieira, Stocco, Ribeiro & Frantz, 2018).

Approximately 0.5% to 3% of patients undergoing surgery will experience infection at or adjacent to the surgical incision site. Compared with patients undergoing surgery who do not have a surgical site infection, those with a surgical site infection are hospitalized approximately 7 to 11 days longer (Seidelman et al, 2023). In addition prevalence of SSI in cardiac surgery was 10% (Maleknejad 2019). About 3% of patients who develop an SSI will die as a result(Awad 2012). Multiple studies confirm that SSIs are a complication with significant sequelae, such as longer hospitalisation, increased health costs, increased morbidity and mortality(Harder et al, 2013; Predin et al 2021).

**Principal Investigator:**

**Name (print      Signature: \_\_\_\_\_ Date: \_\_\_\_\_**

Coronary artery bypass graft (CABG) is one of the surgical procedures for coronary artery disease (CAD) for exhibiting efficacy in reducing mortality rates and enhancing patients' quality of life (Hastalarının, 2019). Moreover, Median sternotomy is a surgical procedure involving a vertical incision through the sternum (breastbone) to access the thoracic cavity. This approach is commonly employed in various cardiac surgeries, including Coronary Artery Bypass Grafting (CABG), valve replacement, and other cardiac procedures. The median sternotomy provides direct access to the heart and great vessels, allowing surgeons to perform interventions with a clear view of the cardiac structures (King et al., 2022). Nevertheless, certain postoperative complications, including delayed healing of chest wounds and persistent incisional pain, adversely impact patients' quality of life while also extending hospital stays and elevating treatment costs.

Wound infections in adult cardiac surgical patients, particularly in the context of median sternotomy, can be influenced by various factors. Identifying and understanding these risk factors is crucial for implementing effective preventive measures (Biancari et al., 2020). Common risk factors include Diabetes Mellitus, obesity, advanced age, immunosuppression, steroid use, preoperative antibiotic prophylaxis, chronic respiratory conditions, sterilization and aseptic techniques, prolonged surgery duration, and peripheral vascular disease (Vieira, Stocco, Ribeiro & Frantz, 2018).

In fact, the prevention and management of wound infections in median sternotomy incisions after adult cardiac surgery are crucial for optimizing patient outcomes, minimizing healthcare costs, and preserving the overall quality of life for individuals undergoing this cardiac surgical procedure (Phoon & Hwang, 2020). Vigilant postoperative care and evidence-based interventions play a key role in achieving these objectives.

Wound dressings play an important role in preventing infections by creating an optimal environment for wound healing and protecting the surgical or injured site from microbial contamination (Oliverius et al., 2021). The primary functions of wound dressings in infection prevention include barrier Protection, moisture management, absorption of exudate, antimicrobial properties, promotion of granulation tissue, reduction of biofilm formation, and promotion of oxygenation (Oliverius et al., 2021).

Effective selection and application of wound dressings depend on various factors, including the type of wound, its stage of healing, and the patient's specific needs. Healthcare professionals should assess wounds, choose appropriate dressings, and monitoring for signs of infection

**Principal Investigator:**

**Name (print)** \_\_\_\_\_ **Signature:** \_\_\_\_\_ **Date:** \_\_\_\_\_

throughout the healing process (Slamborova et al., 2013). Silver dressing is an example of wound dressings that are impregnated or coated with silver or silver-containing compounds. The incorporation of silver in wound dressings is based on the antimicrobial properties of silver ions, which have been recognized for their ability to inhibit the growth of bacteria, fungi, and some viruses.

Many silver dressings are engineered to provide a controlled and sustained release of silver ions over time. This feature ensures a prolonged antimicrobial effect while minimizing the risk of cytotoxicity to healthy cells (Slamborova et al., 2013). Furthermore, although silver dressings are often utilized in the management of chronic wounds, such as diabetic ulcers, pressure ulcers, and venous leg ulcers, however, it can be applied to surgical wounds, including incisions from procedures such as cardiac surgery (e.g., median sternotomy), to reduce the risk of Surgical Site Infections (SSI) (Abbaszadeganet al., 2017). Their antimicrobial properties aid in controlling bacterial load and promoting wound healing. Silver dressings can also help minimize wound-related odors associated with bacterial colonization. This is particularly relevant in wounds with high exudate levels (Woodmansey & Roberts, 2018; Cooper & Kirketerp-Moller, 2018).

These characteristics make silver dressings a valuable tool in the prevention and management of infections in various types of wounds. Silver dressings come in various forms, including gels, foams, films, hydrocolloids, and nanocrystalline dressings. The importance of silver ions in the treatment of chronic and especially infected wounds has been demonstrated in many studies (Woodmansey & Roberts, 2018; Cooper & Kirketerp-Moller, 2018; Dissemend et al., 2017; Li et al., 2017; Walker & Parsons 2014). For example, in 2022, a study was conducted on 218 patients to assess the incidence of incisional surgical site infection and primary healing after general surgery procedures (Lawrie et al., 2022). The study showed that the surgical site infection (SSI) and primary incision healing were reported in 10 (9.2%) versus 21 (19.3%) ( $p = 0.037$ ) and in 95 (87.2%) versus 86 (78.9%) ( $p = 0.107$ ) patients treated with and without silver-based dressing, respectively. Therefore, silver-based dressing demonstrated a lower incidence of incisional SSI and improved primary healing in comparison with patients in whom conventional non-silver-based dressing has been used (Lawrie et al., 2022).

While silver dressings offer significant benefits in wound management, their effect on median sternotomy wound infections in adult patients undergoing cardiac surgery grafting at KFSHRC did

**Principal Investigator:**

**Name (print)** \_\_\_\_\_ **Signature:** \_\_\_\_\_ **Date:** \_\_\_\_\_

not report it. Therefore, **the aim of this study** is to assess the effect of the silver dressing on SSIs rates in adult patients post cardiac surgery.

## Objectives

1. Assess the effectiveness of the silver dressing on SSIs rates as compared to the standard dressing- Mepilex foam dressing in reducing SSIs.

### **Methodology**

*May include: 1. Inclusion Criteria and Exclusion Criteria, which will be used in selecting the research participants; 2. Registration, 3. Randomization Process, 4. Data gathering methods, 5. Procedures, Designated Central Laboratories, 6. Follow-up, 7. Safety and Efficacy Parameters, 8. Expected Outcome, 9. Sample Size, and 10. Statistical Methods.*

## **Research Design**

A single centre randomised control study approach will be followed.

## **Research Setting and study population**

**King Faisal Specialist Hospital and Research Center- Jeddah**, a specialist referral and research center, which is a 390 bedded facility with three main domains of care namely Ambulatory Care (20 units), Nursing Speciality (13 departments), and Nursing General Services (10 departments). Patients admitted to Cardiac surgical intensive unit (CSICU), Coronary Care Unit (CCU) and Cardiovascular Telemetry- Adult (CVT Adult) Unit after cardiac surgery with a sternal wound.

In 2023 there was a total of 150 of adult cardiac patients admitted post cardiac surgery with a mediastinal incision.

[figure not shown]
## **Principal Investigator:**

**Name (print      Signature: \_\_\_\_\_ Date: \_\_\_\_\_**

## Current cardiac SSI rates at KFSHRC-J

SSIs currently are a challenge amongst cardiac surgical patients. The operational benchmarking for SSIs is 2.9 with an operational goal of 2.1. and with the current numbers of SSIs the organisation was not able to outperform the benchmark. The below graph depicts the rates of SSI for the years 2022-2023.

Category	Benchmark	Operational Goal	Year to Date (2023)			Year to Date (2022)		
			No. of Procedures	No. of Infections	Rate	No. of Procedures	No. of Infections	Rate
CABG	2.9	2.1	69	4	5.8	134	8	5.97
All cardiac		2.1	327	4	1.2	734	11	1.5

Despite defined interventions to reduce SSIs such as the **Bundle of Care Interventions for the Prevention of Healthcare associated infections- CIPP 8834 - SSI Prevention Bundle**, the SSI rates for CABG and cardiac have soared in the latter part of 2023.

## Sampling technique

**Principal Investigator:**

**Name (print**      **Signature:** \_\_\_\_\_ **Date:** \_\_\_\_\_

The study will follow a randomised sampling approach. Randomisation will include: first patient transferred from OR to the CSICU will be part of the intervention group, second patient part of the control group. This sequence will be followed until the required sample size is reached.

Sample size will include:

In the year 2023 there were a total of 200 patients admitted for a cardiac surgical procedure requiring a mediastinal incision. Based on this population and sample size calculation- a total of 109 patients will be included – meeting the inclusion and exclusion criteria.

Ie 55 in the intervention group and 54 in the control group.

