### **Exclusion criteria**

- Presence of a concurrent infection and any systemic antibiotic other than those used for the purpose of perioperative prophylaxis.
- Patients who died without an infection within 30 days following surgery.
- Patients who had undergone another procedure through the same incision(s) within a year after enrollment in this study.
- Patients who are a redo- such as needing debridement or an infection.
- Patients that have an open chest
- Patients on ECHMO
- Patients excessively bleeding
- Patients who require the surgery as an emergency
- Patients with a known allergy to silver dressings

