## **Description of intervention**

Intervention will consist of a replacement of the sterile plain postoperative dressing Mepilex border dressing (versatile five-layer all-in-one bordered foam dressing) with the sterile silver-impregnated dressing on 3 units: the CSICU, CVT. The dressing will be applied upon arrival in the CSICU directly on the incision after closure had been performed with sutures and/or staples and the Mepilex border. Dressings will be changed at seven (days) post-surgery (or sooner if oversaturated), and then changed whenever the dressing becomes saturated. Application of the dressing will be discontinued when the incision had epithelialized. There will be no changes in techniques or patient care, and no other changes of any kind (including surgeons) during the entire study period. Throughout the entire period of hospitalization, patients will be monitored for signs and symptoms of infection as per Center for Disease Control [CDC] guidelines ie is superficial, deep, organ space infection (CDC, 2010). Patients will be followed for signs and symptoms of SSIs up to one **month** following surgical intervention. Surgical site infections will be identified through assessment present in chart reviews, clinic visits, readmission to a hospital, laboratory culture surveillance, and telephone interviews at the one month period.

NB: The control group will have the Mepilex foam dressing. All other processes and care will be the same as the intervention group.

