## **Data analysis**

Data analysis will be done using SAS software. Descriptive statistics will include frequencies and percentages. Comparisons between the 2 groups will include chi-square statistic for categorical variables and the t test for continuous variables. Logistic regression will be used to compare the risk of infection according to type of dressing and adjusting for patients' characteristics.

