## **Ethical considerations**

Data will be collected after the necessary approval from Nursing Affairs and the Institutional Review Board. Participation in this study is voluntary and no incentives will be given for participating. Participants are free to withdraw from the study at any point without penalty or risk to the treatment they were entitled to. Information regarding this research study will be offered to the participants in the study both verbally and in the form of an information document and informed consent. All participants in the research study will be selected according to research requirements and treated equally and fairly throughout their participation. Right to privacy and anonymity will be maintained by not linking any personal identification to any of the checklists and all research information will not be traceable back to individuals. Only the researchers will have access to the data, which will be kept on a computer with a password and will be destroyed after five years.

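### The trial is called randomised, but its only allocation rule is strict alternation by order of transfer to the CSICU, so each assignment is predictable and cannot be concealed

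*Protocol*

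**What the plan says.** The label is consistent. Protocol, Research Design: "A single centre randomised control study approach will be followed". The Abstract's Methodology paragraph says patients are randomised, 75 to each group, and the Sampling technique section also calls its approach randomised.

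The mechanism appears only in Sampling technique: "first patient transferred from OR to the CSICU will be part of the intervention group, second patient part of the control group". The section then fixes this for the whole of recruitment: "This sequence will be followed until the required sample size is reached". It gives a total of 109 patients, 55 intervention and 54 control.

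Four other places bear on the point:
- Description of intervention: "The dressing will be applied upon arrival in the CSICU directly on the incision". The dressing therefore goes on at about the moment that sets the patient's place in the sequence.
- Exclusion criteria: "Patients excessively bleeding", with no threshold and no time of assessment.
- Ethical considerations: participants are informed "both verbally and in the form of an information document and informed consent". The text at hand does not say that consent and eligibility must be recorded before the arm is known.
- Data analysis: "Logistic regression will be used to compare the risk of infection according to type of dressing and adjusting for" patients' characteristics.

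**The concern.** Alternation is deterministic. Once the first patient has been assigned, every later arm is fixed. The two arms use different dressings, so the staff who apply them know the last assignment and hence the next. No list can be hidden, because the rule is the list.

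Whoever judges eligibility, obtains consent or influences the order of leaving the operating room can therefore act with the arm in view. Excessive bleeding shows how. It is an unquantified judgement that can arise around the time of transfer, and a doubtful case could be kept or dropped according to which dressing is due next.

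The trial's single objective is a comparison of infection rates between dressings. If inclusion depends on the arm, that comparison mixes the dressing effect with a difference in patient risk. The planned logistic regression helps only for characteristics that are recorded, and reasons for inclusion generally are not. A result reported as randomised would carry more weight than this allocation supports.

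**Working it through.** **1. Is the stated rule really alternation?** Give odd positions to intervention and even positions to control.
- N = 109 (Sampling technique): 55 odd and 54 even positions. This is exactly the stated 55/54.
- N = 150 (Abstract): 75 and 75. This is exactly the stated split.

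The group sizes agree with the literal reading, under which only one sequence is possible.

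**2. Predictability.** Take an observer who knows the scheme and has seen all earlier assignments, and compute the expected share of correct guesses.
- Alternation: 100%, that is 109 of 109 or 150 of 150.
- Simple randomisation: 50%, that is 54.5 of 109 or 75 of 150.
- Permuted block of size 2m, always guessing the arm that is behind: expected correct guesses per block = m + ½ × (2^(2m) / C(2m, m) − 1).

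| Block size | Expected correct per block | Share |
|---|---|---|
| 2 | 1 + ½(4/2 − 1) = 1.500 | 75.0% |
| 4 | 2 + ½(16/6 − 1) = 2.833 | 70.8% |
| 6 | 3 + ½(64/20 − 1) = 4.100 | 68.3% |
| 8 | 4 + ½(256/70 − 1) = 5.329 | 66.6% |

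- Blocks of 4, 6 and 8 in equal frequency: (2.833 + 4.100 + 5.329) / (4 + 6 + 8) = 12.262 / 18 = 68.1%. Simulation of 10,000 lists cut off at the trial's size gave 67.8% at N = 109 (109 × 0.678 ≈ 74 correct) and 68.0% at N = 150 (150 × 0.680 = 102 correct).

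**3. What a random list does to arm sizes.**
- Unstratified blocks of 4, 6 and 8: only the last, incomplete block can be unbalanced. The largest difference between arms is 3 at N = 109 and 4 at N = 150.
- Simple randomisation: N/2 ± 1.96 × √N/2. At N = 109 this is 54.5 ± 10.2, a 95% range of 44 to 65 per arm, or a difference of up to about 21. At N = 150 it is 75 ± 12.0, a range of 63 to 87.

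**4. How few patients could matter.** As an illustration, apply rates given in the protocol to 109 patients.
- All-cardiac site rate in 2023, 1.2%: 109 × 0.012 = 1.3 infections.
- CABG site rate in 2022, 5.97%: 109 × 0.0597 = 6.5 infections.
- Prevalence of 10% cited in the Background: 10.9 infections.

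With event counts in this range, including or leaving out one or two high-risk patients according to arm could change the result.

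**The case against.** Several points can fairly be made on the other side.

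- **The text may be incomplete.** The section says what randomisation will include, which might hint at further steps, and procedures could be described elsewhere. This limits the statements about missing concealment and consent timing to the text at hand. It does not help the rule itself, which is explicit and fixed until recruitment ends. A statistical analysis plan cannot make an alternating sequence random.
- **The 100% figure applies at transfer, to someone who knows the last arm.** At a preoperative consent visit, the order of leaving the operating room may not be settled. That stands as a qualification. With 150 to 200 such patients a year by the protocol's own counts, the next patient will often be obvious.
- **The bleeding example is an inference.** The protocol does not say when that exclusion is judged. This is true, but the defect does not depend on the example.
- **Guess rates are not bias.** They measure predictability, not a shift in the infection comparison. This also stands, and no size of bias is claimed.
- **Blocks remain about 68% guessable where dressings can be seen, and hiding block sizes hardly lowers that average.** This is correct, since guessing the lagging arm needs no knowledge of block size. Hiding the sizes mainly prevents certainty about the last places in a block. The choice between blocks and simple randomisation is therefore open; an unpredictable, concealed sequence is what is needed.

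**Conclusion.** The concern holds. The protocol calls the trial randomised and then prescribes a deterministic allocation that cannot be concealed. From the first patient on, 100% of assignments are predictable at the point of transfer, against 50% under simple randomisation and about 68% under varying blocks of 4, 6 and 8 with every past dressing seen.

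The conclusion rests on reading the allocation rule literally, which the 55/54 and 75/75 group sizes support, and on staff knowing which dressing was used last. It establishes an opportunity for selection bias; whether bias would occur, and in which direction, cannot be derived from the document. Because analysis cannot repair the allocation after enrolment, this must be fixed before the first patient is assigned.

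**What to change.** Replace the alternation sentence in Sampling technique with text such as: *Patients will be allocated 1:1 from a computer-generated random list in randomly varying blocks of 4, 6 and 8, prepared by a person who does not enrol patients. Each assignment stays concealed (sequentially numbered sealed opaque envelopes or a locked electronic form) until consent and the eligibility criteria that can be judged at that time are recorded.*

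Details to settle with it:
- State the moment of opening. On CSICU arrival, just before the dressing is applied, is best, because exclusions that arise during surgery can then be recorded while the arm is still unknown. The qualifier about criteria that can be judged at that time is needed because some listed exclusions concern events after surgery.
- Keep block sizes from enrolling staff and avoid blocks of 2. Simple randomisation is an acceptable alternative and is less guessable. Stratification by CABG is optional.
- If alternation is kept, remove the word randomised from the Abstract, Research Design and Sampling technique, describe the study as quasi-randomised with alternate allocation, and limit the conclusions accordingly.

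The cost is a short amendment plus an envelope set or electronic form. Arm sizes may no longer be exactly 55/54 or 75/75: they can differ by at most 4 with unstratified blocks (more if stratified), or by about 21 at N = 109 with simple randomisation (95% range).

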### **Inclusion criteria**

- Patients 14 years of age and older scheduled for cardiac surgery requiring a sternotomy incision.

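### Allocation by one alternating sequence takes no account of CABG, where the site's own infections concentrate; stratify concealed random lists by CABG and name it as the adjustment factor

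*Protocol*

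**What the plan says.** - **Eligibility** (Protocol, Inclusion criteria): patients "scheduled for cardiac surgery requiring a sternotomy incision". CABG and other operations enter together.
- **Allocation** (Sampling technique): "first patient transferred from OR to the CSICU will be part of the intervention group, second patient part of the control group", repeated until the sample is full. There is one sequence for all operations.
- **Size**: Sampling technique gives "Ie 55 in the intervention group and 54 in the control group". The Abstract gives 75 and 75.
- **Analysis** (Data analysis): a chi-square comparison, and "Logistic regression will be used to compare the risk of infection according to type of dressing" with adjustment for patient characteristics that are not listed.
- **Data collected**: the checklist has a general risk-factor heading and the Parsonnet score. Type of operation is not a listed item.
- **Site SSI rates** (Current cardiac SSI rates at KFSHRC-J), as procedures, infections and rate for 2023 and then 2022: CABG "69 4 5.8 134 8 5.97"; all cardiac "327 4 1.2 734 11 1.5".

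**The concern.** CABG versus other surgery is the only SSI risk factor for which the protocol supplies figures, and it is known before the patient reaches the unit. If CABG carries most of the infections, the arm that happens to receive more CABG patients will tend to show more infections whatever the dressing. With only a few SSIs expected, the reported effect estimate is sensitive to that split, and an open-ended covariate list has too few events to correct it. Tying the arm to arrival order adds a second risk: if the operating list orders cases by type, the CABG split is not left to chance. The protocol does not say how the list is ordered.

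**Working it through.** **1. Reproduce the table.** 4/69 = 5.80%, 8/134 = 5.97%, 4/327 = 1.22%, 11/734 = 1.50%. All four printed rates agree.

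**2. Risk by procedure, both years pooled.**
- CABG: (4+8)/(69+134) = 12/203 = 5.91%.
- Other surgery, assuming CABG is a subset of all cardiac: infections (4−4)+(11−8) = 3; procedures (327−69)+(734−134) = 858; 3/858 = 0.35%.
- Ratio 5.91/0.35 = 16.9. SE of log ratio = √(1/12 − 1/203 + 1/3 − 1/858) = 0.641, so the 95% CI is 4.8 to 59. Fisher p ≈ 5×10⁻⁷.
- 2022 alone: 8/134 against 3/600, ratio 11.9 (3.2 to 44). 2023 alone: no infections outside CABG, so the ratio is undefined.
- If the two rows do not overlap: 5.91% against 15/1061 = 1.41%, ratio 4.2 (2.0 to 8.8).

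**3. Does this carry over to eligible patients?** The 2023 all-cardiac count is 327, but the protocol states only 150 (Research Setting) or 200 (Sampling technique) mediastinal-incision patients that year. Much of the 858 may therefore be ineligible. If the 69 CABG procedures lie within the stated sternotomy population, 2023 gives 4/69 against 0/81 (Fisher p = 0.04) or 0/131 (p = 0.01). The direction survives; the size is not known.

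**4. Chance imbalance at 55/54.** Assumed CABG share s = 69/200 = 34.5% or 69/150 = 46%. The SD of the between-arm difference in share is √[s(1−s)(1/55+1/54)], which assumes simple random allocation. Arm risk = share × 5.91% + (1 − share) × 0.35%, with the shares placed at s ± half the imbalance.

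| | s = 34.5% | s = 46% |
|---|---|---|
| SD of imbalance, points | 9.1 | 9.5 |
| P(imbalance ≥ 10 points, either direction) | 27% | 29% |
| Null arm risks at 10 points | 1.99% v 2.55% | 2.63% v 3.19% |
| Null RR at 10 points (inverse) | 0.78 (1.28) | 0.83 (1.21) |
| P(imbalance ≥ 20 points, either direction) | 3% | 4% |
| Null RR at 20 points | 0.61 | 0.68 |
| Expected SSIs in 109 patients | 2.5 | 3.2 |

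At 75/75 the SDs are 7.8 and 8.1 points, and an imbalance of at least 10 points has a 20-22% chance. With the ratio of 4.2 instead of 16.9, a 10-point imbalance gives a null RR of 0.86-0.88.

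**5. Absolute size.** The shift in risk difference is imbalance × (5.91% − 0.35%) = imbalance × 5.56%.

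| | s = 34.5% | s = 46% |
|---|---|---|
| 1.96-SD imbalance, points | 17.8 | 18.7 |
| Shift in risk difference, points | 0.99 | 1.04 |
| Infections per arm (×55) | 0.55 | 0.57 |
| SE of risk difference, points | 2.9 | 3.2 |
| Chi-square false positives, balanced | 1.9% | 2.9% |
| Chi-square false positives, 1.96-SD imbalance | 2.7% | 3.7% |
| Chi-square false positives, all CABG in one arm | 16% | 29% |

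The false-positive rates come from exact enumeration with no dressing effect. The last row is an extreme that chance would not produce; it bounds what a systematic split could do.

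**The case against.** **Adjustment is planned.** A reader might infer that the analysis ignores CABG. The document does not support that: a covariate-adjusted logistic regression is stated, risk factors and the Parsonnet score are collected, and a covariate list may properly sit in a statistical analysis plan that is not shown. This stands, so the unnamed covariate alone is no error. But with about 2.5 to 3.2 SSIs the model can carry hardly any covariates, so unspecified adjustment is weak protection.

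**The 17-fold figure is fragile.** It rests on three infections outside CABG, on a subset assumption that the table does not state, and on a denominator that probably includes ineligible procedures. This stands, and the figure should be quoted only with its interval and these caveats. It reduces the size; the 2023 counts keep the direction.

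**Chance imbalance does little.** A reader might infer that an ordinary imbalance could mimic or hide a dressing effect. The calculation does not support that. The shift is about half an infection per arm at 1.96 SD, sampling error is about three times as large, and the test does not exceed 5%. Only about half of the 27-29% runs in the direction of apparent benefit. A 20-point imbalance is uncommon, and even then the null RR does not reach the 0.48 (9.2%/19.3%) of the general-surgery study cited in the Background. All of this stands.

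**Other risk factors matter.** The Background lists diabetes, obesity and age among others. CABG stands out partly because it is the only one with figures. This is fair, and is a reason to keep the others for sensitivity analysis.

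**Alternation is the graver fault.** Unstratified allocation would still be valid if it were truly random and concealed. This also stands. Since the allocation paragraph needs rewriting for that reason, adding a stratum costs little.

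**Conclusion.** The point holds in a limited form. Allocation uses one predictable sequence that disregards procedure, while the site's own counts place most infections in CABG: 12 of the 15 recorded over two years if the rows are nested. Under simple random allocation, an imbalance of 10 points or more has a 27-29% chance, and at 10 points it moves the expected null risk ratio to 0.78-0.83 or its inverse. On the risk-difference scale, a 1.96-SD imbalance is worth about 1 point against a standard error of 2.9-3.2. The consequence is an avoidable shift in the point estimate; chance imbalance does not make the test invalid. The larger risk is systematic imbalance if arrival order tracks procedure type, which the protocol neither describes nor rules out.

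The size depends on three assumptions: CABG nested within all cardiac, a CABG share of 35-46%, and pooled 2022-2023 site risks that apply to eligible patients. The last cannot be verified from the document. The change is worth making, but is not critical.

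**What to change.** - **Sampling technique:** replace alternation with concealed random allocation in permuted blocks, using separate lists for CABG yes and CABG no. Leave eligibility unchanged.
- **Data analysis:** name CABG yes/no as the prespecified primary adjustment factor for the SSI comparison, using an exact stratified odds ratio or a penalised logistic model with arm and CABG. Keep the other risk factors and the Parsonnet score for description or sensitivity analysis.
- **Data collection checklist:** record type of operation.

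The cost is one extra allocation list, one checklist item and a line of text. No extra patients or visits are needed, because the procedure is known from the schedule. The change does not remedy the low event count, which needs separate attention.
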